### Study Interventions and Measures:

We will provide one red cell unit of D+ *RH* genotype matched RBCs at the first transfusion study visit. The remainder of units will be provided per clinical standard of care, i.e. D-, CEK-matched, and negative for all other antigens the patient is alloimmunized against. If laboratory monitoring shows no reappearance of anti-D and no signs of increased red cell hemolysis, the patient will receive one unit of D+ *RH* genotype matched RBCs at the 2nd transfusion study visit, and if tolerated, D+ red cell exposures will increase by one unit per study visit until all units required are D+.

---

---

For subjects with a history of stroke/recurrent transient ischemic attack or other indication who require tight control of Hb S and *RH* genotyped blood is not available, standard of care serologic matched blood would be administered rather than delaying transfusion and risking higher Hb S level.

We will collect a pre-transfusion sample to prospectively store plasma on all study subjects.

Study participants will return 5-12 days post-transfusion for a CBC, reticulocyte count, hgb quantification, bilirubin level, and antibody screen to evaluate for anti-D reappearance or red cell hemolysis.

Main study outcome measures are feasibility of identifying sufficient *RH* genotype matched units (identifying sufficient *RH* genotype match red cells without delays in transfusion), and safety (no anti-D reappearance or evidence of hemolysis of transfused red cells).

---

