#### **3.1.2 Intervention visit**

Intervention visits will occur at the time of each of the patient's scheduled transfusion visits. Typically, patients requiring chronic transfusion therapy present for transfusion every 3-5 weeks to maintain their target hemoglobin S level.

At these intervention visits, a member of the research team will obtain an interim medical history, as well as review clinically obtained vital signs and laboratory evaluations. At the time

of pre-transfusion blood draw, IV placement or central line access, 5-10 ml of blood will be drawn for study evaluations (for additional antibody evaluation as needed). Patients will receive their transfusions as ordered for their clinical indication, but will receive red cell units from the blood bank that are *RH* genotype matched in addition to standard C, E, and K antigen matching. Other red cell processing such as irradiation, leukoreduction and/or washing will occur as clinically indicated. We will transfuse one D+ unit matched by *RHD* genotype at the first study visit, increase D+ units incrementally with subsequent transfusion visits, and monitor for anti-D re-demonstration and signs of hemolysis or other adverse effects. Adverse events will be assessed at each of these intervention visits. The next transfusion and intervention visit will be scheduled prior to the subject's discharge from their transfusion visit.

A laboratory visit will be scheduled 5 to 12 days after each transfusion to screen for antibodies and laboratory signs of increased red cell hemolysis from baseline.

If there is an inability to identify sufficient *RH* genotype matched units, standard of care serologic matched red cells will be administered rather than delaying transfusion for more than 7 days.

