### **4.2 Study Treatment Phase**

Intervention visits will be scheduled with each of the subject's transfusion visits as per the subject's clinical indication for chronic transfusion therapy. We will provide one unit of D+ *RH* genotype matched RBCs at the first transfusion study visit (Figure 3). The remainder of units will be D-, CEK-matched, and negative for all other antigens the patient is alloimmunized

---

against. In this manner, should anti-D be re-stimulated, only one unit of the 3 to 11 units required for red cell exchange will be at risk for hemolysis, and the patient would not become

**Figure 3. Example transfusion protocol for D+ patient with history of anti-D** that is not currently detectable, and requires 6 units per RBC exchange every 3 weeks. One D+ unit will be matched by *RHD* genotype and transfused at the first two study visits, and an increasing number of D+ units will be issued at consecutive RBC exchange visits. U, unit. Triangle denotes a study visit for laboratory studies including an antibody screen, CBC, hemoglobin quantification and bilirubin level

acutely anemic. If laboratory monitoring shows no anti-D re-appearance or signs of increased hemolysis, the patient will receive one unit of D+ *RH* genotype matched RBCs at the 2nd transfusion study visit, and again if no anti-D re-appearance or signs of increased hemolysis, we will increase by one D+ unit per study visit until all units are D+. If a patient re-demonstrates anti-D, we will end that subject's participation and he/she will resume transfusions with D negative RBC units.

All patients with SCD on chronic transfusion therapy have a pre-transfusion complete blood count (CBC), Hgb quantification to determine %hgb A and S levels, and an antibody screen. We will collect a pre-transfusion sample to prospectively store plasma on all study subjects. Patients undergoing chronic red cell exchange will have an immediate post-procedure CBC and hgb quantification as standard of care. Study participants will return 5-12 days post-transfusion for a CBC/reticulocyte count, hgb quantification, bilirubin level, and antibody screen to evaluate for anti-D recrudescence or red cell hemolysis (Table 2).

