**Table 2. Laboratory monitoring**

	Pre-transfusion	Immediate Post-transfusion	5-12 days Post-transfusion
Complete blood count	✓	✓	✓
Hemoglobin quantification	✓	✓	✓
Reticulocyte count	✓		✓
Antibody screen/identification	✓		✓
Bilirubin (total, unconjugated)			✓
Creatinine			✓
Plasma sample frozen	✓		✓
Donor red cells frozen	✓		

Any time a patient shows a re-appearance of anti-D on an antibody screen, the medical monitor will be notified, and all safety data will be reviewed. As stated above, if a subject re-demonstrates anti-D, we will end that subject's participation and he/she will resume transfusions with D negative RBC units.

If any subject shows signs of transfused red cell hemolysis, with or without an anti-D identified on the antibody screen, the medical monitor will be notified, and all safety data will be reviewed.

Study stopping criteria include:

- 1) Two of the first 5 enrolled subjects, or after the first 5 enrolled subjects, greater than 30% of enrolled patients, develop re-appearance of anti-D
- 2) Any subject with anti-D re-appearance and clinical or laboratory evidence of transfused red cell hemolysis (dark urine, increased scleral icterus, exacerbated anemia, higher Hb S level than expected based on timing from last transfusion

If either of these criteria occur, the study will be stopped, the safety medical monitor will review all clinical and laboratory evidence to determine safety risks, and will meet with the investigative team to determine a safe course of action. The IRB would be notified and the study procedures would be suspended until approval of the IRB.

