**5.2 Safety Evaluation**

Subject safety will be monitored by adverse events, vital signs, anti-D reappearance and other laboratory data (complete blood count, hemoglobin quantifications, red cell antibody evaluations). It will also include evaluation for any delays in transfusion of red cells. If a patient re-demonstrates anti-D, we will end that subject's participation and he/she will resume transfusions with D negative RBC units.

We will have a medical monitor independent of the study team who is familiar with SCD and transfusion, and blood bank procedures. The medical monitor will review safety data, including antibody screens for anti-D reappearance, and other laboratory studies, i.e blood counts and hemoglobin quantifications, for signs of transfused red cell hemolysis. Details about the units transfused, including the *RH* genotype, and the red cell antigen profile, will be reviewed.

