#### 6.2.2 Efficacy Analysis

The primary efficacy endpoints will be anti-D re-appearance, signs of increased hemolysis, and timely issue of units for transfusion. These will be descriptive data.

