## 8 SAFETY MANAGEMENT

### 8.1 Clinical Adverse Events

Clinical adverse events (AEs) will be monitored throughout the study.

We will have a medical monitor independent of the study team who is familiar with SCD and transfusion, and blood bank procedures. The medical monitor will review safety data, including antibody screens for anti-D reappearance, and other laboratory studies, i.e blood counts and hemoglobin quantifications, for signs of transfused red cell hemolysis. Details about the units transfused, including the *RH* genotype, and the red cell antigen profile, will be reviewed.

Any time a patient shows a re-appearance of anti-D on an antibody screen, the medical monitor will be notified, and all safety data will be reviewed. As stated above, if a subject re-demonstrates anti-D, we will end that subject's participation and he/she will resume transfusions with D negative RBC units.

If any subject shows signs of transfused red cell hemolysis, with or without an anti-D identified on the antibody screen, the medical monitor will be notified, and all safety data will be reviewed.

Study stopping criteria include:

- 1) Three of the first 5 enrolled subjects, or greater than 50% of enrolled patients, develop re-appearance of anti-D
- 2) Any subject with anti-D re-appearance and clinical or laboratory evidence of transfused red cell hemolysis (dark urine, increased scleral icterus, exacerbated anemia, higher Hb S level than expected based on timing from last transfusion)

If either of these criteria occur, the study will be stopped, the safety medical monitor will review all clinical and laboratory evidence to determine safety risks, and will meet with the investigative team to determine a safe course of action. The IRB would be notified and the study procedures would be suspended until approval of the IRB.

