If either of these criteria occur, the study will be stopped, the safety medical monitor will review all clinical and laboratory evidence to determine safety risks, and will meet with the investigative team to determine a safe course of action. The IRB would be notified and the study procedures would be suspended until approval of the IRB.

The PI will monitor study progress, ensure subject safety, and the accuracy and security of the data at CHOP, and will report any adverse events in accordance with the FDA regulations as they pertain to blood products and IRB policies.

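### Hemolysis of transfused cells in which anti-D is never detected has no pre-specified study-level stop, because both listed stopping criteria require anti-D re-appearance

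*Combined protocol and SAP*

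**What the plan says.** Safety has two components. The abstract, under study interventions and measures, defines it as "safety (no anti-D reappearance or evidence of hemolysis of transfused red cells". Section 6.2.2 also keeps them apart: "The primary efficacy endpoints will be anti-D re-appearance, signs of increased hemolysis, and timely issue of units for transfusion".

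Sections 4.2, 8.1 and 9.3.1 each set out monitoring and then a stopping list. Before the list, each covers the subject who shows "signs of transfused red cell hemolysis, with or without an anti-D identified on the antibody screen, the medical monitor will be notified", with a review of all safety data to follow.

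The list then has two entries. Criterion 1 counts subjects with anti-D re-appearance. Criterion 2 is "Any subject with anti-D re-appearance and clinical or laboratory evidence of transfused red cell hemolysis", with dark urine, scleral icterus, worse anemia and an unexpectedly high Hb S given as examples of the evidence. The consequence paragraph reads "If either of these criteria occur, the study will be stopped". It continues with monitor review, a meeting with the investigators, IRB notification, and suspension of procedures until the IRB approves.

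Section 5.2 gives the monitor's role: "The medical monitor will review safety data, including antibody screens for anti-D reappearance, and other laboratory studies". It does not mention authority to halt the study.

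**The concern.** The authors saw that transfused cells might be hemolyzed without a detectable anti-D, and wrote a response for the individual case. They did not carry that event into the stopping list. One of the two stated safety outcomes therefore has no study-level boundary when it occurs alone.

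If one subject has a serious hemolytic event with screens negative for anti-D, or if several subjects hemolyze in this way, the monitor reviews each case. The protocol then names no point at which the remaining subjects stop receiving D+ units until the IRB has looked. Exposure also grows during the study. The argument in 4.2 that only one unit is at risk applies to the early visits, and by the last step every unit is D+.

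**Working it through.** The plan states no operating characteristics for its stopping rule, so there is no figure to reproduce. The check is logical, followed by arithmetic on exposure and on the proposed fix.

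**1. The two criteria against the four possible states of a subject.**

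| Anti-D | Hemolysis | Counts toward criterion 1 | Meets criterion 2 |
|---|---|---|---|
| no | no | no | no |
| no | yes | no | no |
| yes | no | yes | no |
| yes | yes | yes | yes |

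The second row is the gap. Adding more subjects of that kind leaves the criterion 1 count at zero and criterion 2 false. The thresholds in criterion 1 differ between sections (two of the first five, then over 30%, in 4.2 and 9.3.1; three of the first five, or over 50%, in 8.1). That inconsistency is a separate matter and does not change the result.

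**2. How narrow the gap is.** Criterion 2 does not require both findings on the same day. Table 2 has an antibody screen at 5-12 days and another before each transfusion, and section 3.1.2 says that "patients requiring chronic transfusion therapy present for transfusion every 3-5 weeks". Hemolysis first seen with a negative screen therefore meets criterion 2 if anti-D shows up later. Only hemolysis in which anti-D is never found stays outside.

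**3. What else applies to such a case.**

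| Safeguard | Section | Sets a pause for other subjects? |
|---|---|---|
| Monitor notified, all safety data reviewed | 4.2, 8.1, 9.3.1 | No |
| The subject's own D+ step: "again if no anti-D re-appearance or signs of increased hemolysis, we will increase by one D+ unit per study visit" | 4.2 | No |
| Investigator may withdraw subjects for AEs or safety | 4.5 | No; discretionary |
| SAE and unanticipated-problem reporting | 8.2, 8.5 | No; reporting only |
| IRB review before children enroll | 3.1 | Once only, with no hemolysis threshold |

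**4. Occasions to observe the event.** With N units per visit, one D+ unit at visits 1 and 2 and one more at each later visit, all units are D+ at visit N + 1. Section 9.3.2 gives a typical N of 3 to 8, hence 4 to 9 visits per subject. If all 20 subjects complete, that is 20 × 4 = 80 to 20 × 9 = 180 transfusion visits, each followed by a 5-12 day check.

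**5. How a third criterion would behave (rates assumed).** Let p be the per-subject probability of a case that the monitor accepts as at least possibly related, s the fraction that are serious, and n the number of subjects. For a pause after one serious case or two subjects with any case:

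P(pause) = 1 − (1−p)^n − n·p·(1−p)^(n−1)·(1−s)

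For n = 20 and p = 0.05 this is 1 − 0.3585 − 0.3774·(1−s).

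| Assumed p | n = 20, none serious | n = 20, all serious | n = 5, none serious | n = 5, all serious |
|---|---|---|---|---|
| 2% | 6.0% | 33.2% | 0.4% | 9.6% |
| 5% | 26.4% | 64.2% | 2.3% | 22.6% |
| 10% | 60.8% | 87.8% | 8.1% | 41.0% |
| 20% | 93.1% | 98.8% | 26.3% | 67.2% |

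Under the listed criteria the corresponding probability of a pre-specified stop is 0 at every p. The table describes the rule, not the likely course of the trial.

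**6. Why unadjudicated laboratory signs should not count.** Section 5.1.5 lists lower hemoglobin, lower hgb A with higher hgb S, and raised bilirubin, without cut-offs. Suppose a fraction q of visits shows such signs, independently, over v visits, so that p = 1 − (1−q)^v. The chance that two or more of 20 subjects are flagged, with no serious case and before any monitor exclusion, is:

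| Assumed q | v = 4 | v = 9 |
|---|---|---|
| 1% | p = 0.039, 19% | p = 0.086, 53% |
| 2% | p = 0.078, 47% | p = 0.166, 87% |

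A rule that counted these signs by default could pause the study often for noise.

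**The case against.** The best defense is that the omission is deliberate and sensible. The added risk of the intervention is recall of anti-D, and the criteria target it. Hemolysis without anti-D is hard to attribute, because D- units are given at the same visits until the last step and these patients often carry other antibodies. In a descriptive, single-center pilot of about 20 subjects, sending such cases to an independent monitor is a reasonable alternative to an automatic stop. Each list is also introduced with the verb *include*, and the consequence paragraph makes the two criteria sufficient for a stop without calling them the only grounds. The investigator may withdraw subjects for safety under 4.5, and a serious, related and unanticipated event reaches the IRB within 24 hours or 7 days under 8.5.

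Much of this stands. A reader might infer that the study could not be paused for hemolysis without anti-D, or that such hemolysis goes unwatched. The documents support neither reading: a discretionary pause is open, and every case is reviewed. The attribution argument also stands, and it is why the fix should rest on the monitor's judgement.

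It does not close the gap. A discretionary pause is not a pre-specified one, and no section says that the monitor may order it. Withdrawal under 4.5 sets no count or event that would pause the others' D+ units. Prompt IRB notice is limited to unanticipated events, while increased hemolysis is a named risk in 9.3.1 and could be judged anticipated. Non-serious cases may wait for continuing review.

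**Conclusion.** The point holds in a limited form and should be fixed. For hemolysis in which anti-D is never detected, the protocol has no pre-specified study-level stop, for any number of subjects. This follows from the wording of the criteria and needs no assumption about rates. Confidence in it is high.

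The practical size cannot be stated. The documents give no rate for such hemolysis, and the percentages in the working rest on assumed rates. They show neither that the event is likely nor how often the proposed rule would pause this trial. The case for a change rests on three facts: the protocol makes hemolysis a safety outcome in its own right, it rates the study as greater than minimal risk, and it already collects what a boundary would need.

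**What to change.** In 4.2, 8.1 and 9.3.1, add a third criterion under the existing consequence paragraph, along these lines: *transfused red cell hemolysis after a D+ study unit, with or without detected anti-D, showing the signs listed in criterion 2 and judged by the independent medical monitor as at least possibly related to the D+ units, pauses the study after one serious case or after two subjects with any such case.* The sponsor and monitor may choose another small count, provided that it is fixed in advance. The laboratory signs in 5.1.5 may inform the monitor's judgement but should not make a case by themselves. State also that the monitor may halt the study.

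The cost is an amendment to three sections and a documented attribution decision for each case. No new tests are needed, since Table 2 already provides the hemolysis labs, the antibody screens, and stored plasma and donor cells. The downside is an occasional temporary pause, lifted only with IRB approval, for an event later judged unrelated. How often that would happen cannot be estimated from the documents.

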#### **4.2.1 Visit 1**

At each intervention visit the following procedures and measurements include:

- Interim medical history
- Medication review
- Review of vital signs
- Review of clinical laboratory evaluation
- Peripheral blood sample collection
- Transfusion of 1 unit D+ *RH* genotype matched red cell units. Remainder of units transfused will be serologic CEK matched red cells that are D negative.
- Adverse event assessment

#### **4.2.2 Visit 2**

- Laboratory tests (see table 2)
- Assess possible adverse events

#### **4.2.3 Visit 3 plus**

- Same as Visit 1, keep repeating until all units transfused are D+ or anti-D reappearance

### **4.3 Follow-up Phase**

The follow-up phase involves medical chart review and will continue for up to 6 months after the subject's last transfusion and intervention visit. The medical chart review will abstract data regarding the transfusion visit, as well as blood bank evaluations including antibody screens and antibody identification.

#### **4.3.1 End of Study**

There are no special procedures for the end of study participation.

---

#### **4.4 Unscheduled Visits**

We do not anticipate unscheduled visits but these will be recorded. If a patient presents to Emergency Department, or is admitted to the Inpatient Hospital service, and requires transfusion, we will order D- red cells matched for C, E, and K by standard serologic methods which is the standard of care.

#### **4.5 Subject Completion/Withdrawal**

Subjects may withdraw from the study at any time without prejudice to their care. They may also be discontinued from the study at the discretion of the Investigator for lack of adherence to study treatment or visit schedules, or AEs. The Investigator may also withdraw subjects who violate the study plan, or to protect the subject for reasons of safety or for administrative reasons. It will be documented whether or not each subject completes the clinical study. If the Investigator becomes aware of any serious, related adverse events after the subject completes or withdraws from the study, they will be recorded in the source documents and on the CRF.

##### **4.5.1 Early Termination Study Visit**

Subjects who withdraw from the study will have all procedures enumerated for the last transfusion/intervention as the early termination visit.

## 5 STUDY EVALUATIONS AND MEASUREMENTS

### 5.1 Screening and Monitoring Evaluations and Measurements

#### 5.1.1 Medical Record Review

The following variables will be abstracted from the medical chart (paper or electronic).

- Date of birth
- Height and weight
- Vital signs (temperature, blood pressure, heart rate, respiratory rate)
- Medications
- Medical history including SCD clinical course, complications, and indication for chronic red cell transfusion therapy
- Transfusion and blood bank history including date of first transfusion, number of lifetime red cell exposures, alloimmunization history, antibody evaluations, history of transfusion reactions, *RH* genotype, extended red cell antigen profiles
- Additional clinical laboratory studies including complete blood counts, reticulocyte counts, antibody evaluations, direct antiglobulin test, chemistry panels, lactate dehydrogenase levels

#### 5.1.2 Physical Examination

A physical examination will be performed for the baseline assessment.

#### 5.1.3 Vital Signs

Vital signs (temperature, blood pressure, heart rate, respiratory rate) will be measured as part of clinical care. The study team will review and record the vital signs from the chart.

